4.0 STAGING CRITERIA

Staging criteria are not applicable to this study.

5.0 ELIGIBILITY CRITERIA

Each of the criteria in the following section must be met in order for a patient to be considered eligible for registration. Use the spaces provided to confirm a patient's eligibility. For each criterion requiring test results and dates, please record this information on the Onstudy Form and submit via Medidata Rave® (see [Section 14.0](#)). Any potential eligibility issues should be addressed to the Data Operations Center in Seattle at [name] prior to registration.

In calculating days of tests and measurements, the day a test or measurement is done is considered Day 0. Therefore, if a test is done on a Monday, the Monday 4 weeks later would be considered Day 28. This allows for efficient patient scheduling without exceeding the guidelines. **If Day 7 or 28 falls on a weekend or holiday, the limit may be extended to the next working day.**

SWOG Patient No. _____

Patient's Initials (L, F, M) _____

5.1 Step 1 Initial Registration: BRAF^{V600E} Testing

If patient has already had BRAF testing, he or she must satisfy these eligibility criteria before being considered for Step 2 Randomization.

a. Disease Related Criteria

_____ 1. Patients must have histologically or cytologically documented adenocarcinoma of the colon or rectum that is either metastatic, or locally advanced and unresectable. NOTE: In the event that both cecal and appendiceal primaries are considered, patient is eligible if it is concluded by the treating oncologist to most likely be cecal based on pathological, surgical, and clinical interpretation. Clinical diagnosis must be clearly documented in the "Comments" section on the **S1406** Onstudy Form.

_____ 2. Patients must have BRAF^{V600E} mutant status documented by a CLIA certified laboratory on a pathology report prior to Step 2 registration. Use of an FDA-approved test is preferred although other BRAF tests at a CLIA-certified laboratory will also be accepted.

If a BRAF^{V600E} mutation is known, then the patient must be registered to Step 2 Randomization immediately following Step 1 Initial Registration.

If testing has not been performed locally, BRAF^{V600E} testing must be completed by the central lab (see [Section 15.1](#)) prior to Step 2 Randomization. If the specimen does not have a BRAF^{V600E} mutation, the patient is ineligible for Step 2 Randomization.

_____ 3. Brain metastases are allowed if they have been adequately treated with radiotherapy or surgery and stable for at least 90 days prior to Step 1 Initial Registration. Eligible patients should be neurologically asymptomatic and without corticosteroid treatment for at least 7 days prior to Step 1 Initial Registration.

_____ 4. Patients must have had one or two prior regimens of systemic chemotherapy for metastatic or locally advanced, unresectable disease. (A maintenance regimen of 5-fluorouracil or capecitabine, with or without bevacizumab, should not be counted as a separate line of treatment.) Prior treatment with irinotecan is allowed. Prior treatment for metastatic disease is not required for patients who experienced disease recurrence during or within 6 months of completion of adjuvant chemotherapy.

SWOG Patient No. _____

Patient's Initials (L, F, M) _____

5.1 Step 1 Initial Registration: BRAF^{V600E} Testing (contd.)

_____ 5. Patients must not have been treated with any of the following prior to Step 1 Initial Registration:

- Cetuximab, panitumumab, or any other monoclonal antibody against EGFR or inhibitor of EGFR.
- BRAF inhibitor including, but not limited to, vemurafenib or dabrafenib. Regorafenib is not considered a BRAF inhibitor for the purpose of determining trial eligibility.
- MEK inhibitor including, but not limited to, trametinib or selumetinib.

_____ 6. Known KRAS or NRAS mutations:

- a. All patients must have molecular testing performed in a clinical lab which includes codon 12 and 13 of KRAS. Patients with any mutation in codon 12 and 13 of KRAS are not eligible for the protocol.
- b. Testing for additional codons in KRAS or testing for NRAS is not required. However, if such testing has been performed in a clinical lab and any mutation in codons 61 or 146 in KRAS, or codons 12, 13, 61, or 146 in NRAS is detected, the patient is not eligible for the protocol.

b. Specimen Submission Criteria

_____ 1. Patients must have tumor (slides or block) available for submission for V600E BRAF testing as described in [Section 15.1](#).

_____ 2. Patients must have additional tumor available and be willing to submit tissue and blood samples as described in [Section 15.2](#).

c. Regulatory Criteria

_____ 1. Patients or their legally authorized representative must be informed of the investigational nature of this study and must sign and give written informed consent in accordance with institutional and federal guidelines. For Step 1 Initial Registration of patients who have not yet submitted specimens for the central BRAF^{V600E} testing, the appropriate consent form is the Step 1 Consent Form. For both Step 1 Initial Registration and Step 2 Randomization of patients whose BRAF mutation status is already known, the appropriate consent form is the Step 2 Consent Form.

SWOG Patient No. _____

Patient's Initials (L, F, M) _____

5.2 Step 2 Randomization

Patients with known BRAF mutation must be registered to Step 2 Randomization immediately following Step 1 Initial Registration. Results of BRAF testing will be available on the SWOG Specimen Tracking Website within 10 calendar days from submission of tissue specimen to Moffitt Cancer Center and patient must be registered to Step 2 within 60 days of Step 1 Initial Registration.

a. Clinical/Laboratory Criteria

- _____ 1. Patients must have BRAF^{V600E} mutation.
- _____ 2. Patients must have measurable or non-measurable disease that is either metastatic or locally advanced and unresectable, as defined in [Section 10.1](#). CT scans or MRIs used to assess all disease must have been completed within 28 days prior to Step 2 Randomization. CT scans or MRIs must be assessed and documented on the Baseline Tumor Assessment Form (RECIST 1.1).
- _____ 3. Previous chemotherapy, immunotherapy, or radiation therapy must have been completed at least 14 days prior to Step 2 Randomization and all toxicity must be resolved to CTCAE v4.0 Grade 1 (with the exception of CTCAE v4.0 Grade 2 neuropathy) prior to Step 2 Randomization.
- _____ 4. Patients must have a Zubrod Performance Status of 0-1. (See [Section 10.4](#).)
- _____ 5. Patients must be ≥ 18 years of age.
- _____ 6. Patients must have a complete physical examination and medical history within 28 days prior to Step 2 Randomization.
- _____ 7. Patients must have adequate hematologic function as evidenced by all of the following within 14 days prior to Step 2 registration: ANC ≥ 1,500/mcL; platelets ≥ 100,000/mcL; and hemoglobin ≥ 9 g/dL.
- _____ 8. Patients must have adequate hepatic function as evidenced by all of the following within 14 days prior to Step 2 registration: AST and ALT ≤ 2.5 x Institutional Upper Limit of Normal (IULN) or ≤ 5 x IULN if liver metastases are present; and total bilirubin ≤ 1.5 x IULN.
- _____ 9. Patients must have adequate kidney function as evidenced by at least ONE of the following:
 - Serum creatinine ≤ 1.5 x IULN within 14 days prior to Step 2 Randomization OR
 - Calculated creatinine clearance > 60 ml/min. The serum creatinine value used in the calculation must have been obtained within 14 days prior to Step 2 Randomization.

Calculated creatinine clearance = $\frac{(140 - \text{age}) \times \text{wt (kg)} \times [0.85 \text{ (if female)}]}{72 \times \text{creatinine (mg/dL)}}$
- _____ 10. Patients must have an ECG within 14 days prior to Step 2 Randomization. Patients must have QTc ≤ 500 msec.

SWOG Patient No. _____

Patient's Initials (L, F, M) _____

5.2 Step 2 Randomization (contd.)

- _____ 11. Patients must not have a known history of Gilbert's Syndrome or known homozygosity for the UGT1A1*28 allele.
- _____ 12. Patients must not have interstitial pneumonia or extensive symptomatic interstitial fibrosis of the lung.
- _____ 13. Patients must not have an uncontrolled intercurrent illness including, but not limited to, active bleeding diathesis, uncontrolled infection/disorders, nonmalignant medical illnesses that are uncontrolled or whose control may be jeopardized by the treatment with the study therapy, or psychiatric illness/social situations which would limit compliance with study requirements.
- _____ 14. Patients must be able to swallow pill/tablet and have no refractory nausea, vomiting, malabsorption, external biliary shunt, or significant small bowel resection that would preclude adequate absorption.
- _____ 15. Patients must not be pregnant or nursing due to risk of fetal or nursing infant harm. Women/men of reproductive potential must have agreed to use an effective contraceptive method while on study and for at least 60 days after study treatment. A woman is considered to be of "reproductive potential" if she has had menses at any time in the preceding 12 consecutive months. In addition to routine contraceptive methods, "effective contraception" also includes heterosexual celibacy and surgery intended to prevent pregnancy (or with a side-effect of pregnancy prevention) defined as a hysterectomy, bilateral oophorectomy or bilateral tubal ligation. However, if at any point a previously celibate patient chooses to become heterosexually active during the time period for use of contraceptive measures outlined in the protocol, he/she is responsible for beginning contraceptive measures.
- _____ 16. No other prior malignancy is allowed except for the following: adequately treated basal cell or squamous cell skin cancer, *in situ* cervical cancer, adequately treated Stage I or II cancer from which the patient is currently in complete remission, or any other cancer from which the patient has been disease free for three years.

b. Regulatory Criteria

- _____ 1. Patients or their legally authorized representative must be informed of the investigational nature of this study and must sign and give written informed consent in accordance with institutional and federal guidelines. For all patients, the appropriate consent form for this registration is the Step 2 Consent Form.
- _____ 2. As a part of the OPEN registration process (see [Section 13.4](#) for OPEN access instructions) the treating institution's identity is provided in order to ensure that the current (within 365 days) date of institutional review board approval for this study has been entered in the system.

SWOG Patient No. _____

Patient's Initials (L, F, M) _____

5.2 Step 2 Randomization (contd.)

c. Specimen Submission Criteria

- _____ 1. Patients (at institutions listed in [Section 15.4](#) only) must be offered the opportunity to participate in the optional **S1406** Co-Clinical PDX Model Trial (see [Section 15.4](#)). Participating patients must have a fresh tissue biopsy for the Co-Clinical PDX Model Trial completed within 7 days of Step 2 Randomization.

5.3 Step 3 Crossover Registration

- _____ a. Patients must have documented disease progression as defined in [Section 10.2d](#) while on Arm 1 of this protocol. The Follow-up Tumor Assessment Form documenting disease progression must be submitted to SWOG prior to Step 3 Crossover Registration. Registration to Step 3 Crossover must be within 28 days of discontinuation of Arm 1 protocol treatment. Patients going off treatment for any other reason are not eligible.
- _____ b. Patients must have a Zubrod Performance Status of 0-1. (See [Section 10.4](#))
- _____ c. Patients must have adequate hematologic function as evidenced by all of the following within 14 days prior to Step 3 registration: ANC \geq 1,500/mcL; platelets \geq 100,000/mcL; and hemoglobin \geq 9 g/dL.
- _____ d. Patients must have adequate hepatic function as evidenced by all of the following within 14 days prior to Step 3 registration: AST and ALT \leq 2.5 x Institutional Upper Limit of Normal (IULN) or \leq 5 x IULN if liver metastases are present; and total bilirubin \leq 1.5 x IULN.
- _____ e. Patients must have adequate kidney function as evidenced by at least ONE of the following:
- Serum creatinine \leq 1.5 x IULN within 14 days prior to Step 3 registration OR
 - Calculated creatinine clearance $>$ 60 ml/min. The serum creatinine value used in the calculation must have been obtained within 14 days prior to Step 3 registration.

$$\text{Calculated creatinine clearance} = \frac{(140 - \text{age}) \times \text{wt (kg)} \times [0.85 \text{ (if female)}]}{72 \times \text{creatinine (mg/dL)}}$$

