7.4 Drug Compliance Documentation

Drug compliance for vemurafenib will be recorded by patients in an Intake Calendar (see [S1406](#) protocol abstract page on the SWOG website [www.swog.org] for an example). Institutional CRAs will review and ascertain patient adherence with protocol therapy at the end of treatment for each cycle. Calendar should be kept in the patient's clinic chart. Note that the Intake Calendar is provided only as a tool for tracking patient compliance. Sites may utilize institutional pill diaries or other source documentation in place of the Intake Calendar at the discretion of the treating physician.

7.5 Crossover following disease progression on Arm 1

- a. Following radiographic documentation by RECIST 1.1 (in [Section 10.2d](#)) of disease progression, patients initially randomized and treated on Arm 1 may register to Step 3 Crossover Registration to be treated with vemurafenib, irinotecan, and cetuximab per the schedule and doses listed below. Patients must be eligible and registered for Step 3 Crossover Registration per [Section 5.3](#). Patients must be re-staged at time of progression on Arm 1 prior to registration to Step 3 Crossover Registration. Follow-up for these patients after crossover will be the same as those patients initially randomized to Arm 2.

b. Treatment – Arm 3

Patients who are registered to Step 3 Crossover Registration will receive the following treatment until meeting one of the criteria in [Section 7.6](#).

Agent	Dose**	Route	Day	Schedule*
Cetuximab	500 mg/m ²	IV over 60 min	1, 15	Prior to irinotecan
Irinotecan	180 mg/m ²	IV over 90 min	1, 15	After cetuximab
Vemurafenib	960 mg (1920 mg total daily dose)	PO BID	1-28	Daily

* Note: One cycle = 28 days

** If patient was on a reduced dose of cetuximab and/or irinotecan in Arm 1, he or she should begin treatment at that dose in Arm 3.

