* For reporting these events: NCI CTCAE 4.0 defines these reactions differently: "Cytokine release syndromes/acute infusion reactions are different from allergic/hypersensitivity reactions, although some of the manifestations are common to both AEs. An acute infusion reaction may occur with an agent that causes cytokine release (e.g., monoclonal antibodies or other biological agents). Signs and symptoms usually develop during or shortly after drug infusion and generally resolve completely within 24 hours of completion of infusion." See the "Syndromes" section of the CTCAE version 4.0 for a complete list of signs and symptoms of "Cytokine release syndrome/acute infusion reaction;" and see the "Allergy/Immunology" section for a description of hypersensitivity.

CLOSED EFFECTIVE 04/10/2016

o. Electrocardiogram QT Corrected Interval Prolonged

Toxicity Grade	Dose Modification
3 or 4	Withhold vemurafenib until QTc interval \leq 500 msec and resume therapy at one reduced dose level. Permanently remove from protocol treatment if the QTc remains $>$ 500 msec and increased $>$ 60 msec from pre-treatment values after controlling cardiac risk factors for QT prolongation (e.g., electrolyte imbalances, congestive heart failure, bradyarrhythmias).

p. Development of new keratoacanthomas or squamous cell carcinoma of the skin

All patients receiving vemurafenib are recommended to undergo a dermatologic evaluation and head/neck examination by their treating physician for monitoring of keratoacanthomas and squamous cell carcinomas. This evaluation should be done at baseline and every 2 months on therapy. CT imaging of the chest, which is performed at baseline and every 2 months on treatment for disease assessment, should be evaluated for any findings of concern for non-dermatologic squamous cell carcinomas. These evaluations should continue for 6 months after completion of vemurafenib, if deemed clinically appropriate by the treating physician. Any new skin lesions or head/neck/chest findings must be treated appropriately, as directed by a dermatologist or otolaryngologist as indicated, while receiving therapy on this protocol. Patients who develop keratoacanthomas or new squamous cell carcinomas of the skin while being treated on protocol should be managed by removal of the carcinomas by a dermatologist. If the lesions are unable to be removed due to the number or location, then the patient should be removed from all protocol therapy.

q. Hypomagnesemia

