9.1 Arm 1: Cetuximab + Irinotecan

REQUIRED STUDIES	Step 1 Initial Reg	Step 2 Rand	Cycle 1				Cycle 2				Cycle 3				Cycle 4				Ω FU prior to prog	% α FU after prog
			W 1	W 2	W 3	W 4	W 5	W 6	W 7	W 8	W 9	W 10	W 11	W 12	W 13	W 14	W 15	W 16		
PHYSICAL ∑																				
History and Physical Exam		X	X		X		X		X		X		X		X		X		X	X
Weight and Performance Status		X	X		X		X		X		X		X		X		X		X	X
Toxicity Notation					X		X		X		X		X		X		X		X	X
Disease Assessment		X									X								X	X
LABORATORY ∑																				
CBC/Differential/Platelets		X			X		X		X		X		X		X		X			
AST and ALT		X			X		X		X		X		X		X		X			
Serum creatinine/ Calculated creatinine clearance		X			X		X		X		X		X		X		X			
Total bilirubin		X			X		X		X		X		X		X		X			
Magnesium/ Potassium Calcium/Sodium/Bicarb/ Chloride		X			X		X		X		X		X		X		X			
SPECIMEN SUBMISSION																				
Tissue for BRAF Testing & Banking £	X																			
Blood £	X										X								X	X
Fresh Tissue Biopsy ζ		X																		
X-RAYS AND SCANS																				
CT or MRI for Disease Assessment ◇		X									X								X	X
ECG		X																		
TREATMENT ∑																				
Cetuximab			X		X		X		X		X		X		X		X			
Irinotecan			X		X		X		X		X		X		X		X			

Click here for [footnotes](#).

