9.2 Arm 2: Cetuximab + Irinotecan + Vemurafenib

REQUIRED STUDIES	Step 1 Initial Reg	Step 2 Rand	Cycle 1				Cycle 2				Cycle 3				Cycle 4				Ω FU prior to prog	% FU after prog
			W 1	W 2	W 3	W 4	W 5	W 6	W 7	W 8	W 9	W 10	W 11	W 12	W 13	W 14	W 15	W 16		
PHYSICAL ∑																				
History and Physical Exam		X ¥	X		X		X		X		X		X		X		X		X	
Weight and Performance Status		X	X		X		X		X		X		X		X		X		X	
Toxicity Notation					X		X		X		X		X		X		X		X	
Disease Assessment		X												X					X	
Dermatologic evaluation ~		X					X							X					X	
Head and Neck Exam †		X					X							X					X	
LABORATORY ∑																				
CBC/Differential/Platelets		X			X		X		X		X		X		X		X			
AST and ALT		X			X		X		X		X		X		X		X			
Serum creatinine/ Calculated creatinine clearance		X			X		X		X		X		X		X		X			
Total bilirubin		X			X		X		X		X		X		X		X			
Magnesium/ Potassium Calcium/Sodium/Bicarb/Chlo ride		X			X		X		X		X		X		X		X			
SPECIMEN SUBMISSION																				
Tissue for BRAF Testing & Banking £	X																			
Blood £	X										X								X	X
Fresh Tissue Biopsy ¯		X																		
X-RAYS AND SCANS																				
CT or MRI ◇ ϖ		X									X								X	X
ECG ø		X			X				X				X							
TREATMENT ∑																				
Cetuximab			X		X		X		X		X		X		X		X			
Irinotecan			X		X		X		X		X		X		X		X			
Vemurafenib			X	X	X	X	X	X	X	X	X	X	X	X	X	X	X	X	X	X

Click here for [footnotes](#).

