9.3 Arm 3: Cetuximab + Irinotecan + Vemurafenib

REQUIRED STUDIES	Step 3 Cross- over Reg	Cycle 1				Cycle 2				Cycle 3				Cycle 4				Ω FU prior to Prog	% FU after Prog
		W	W	W	W	W	W	W	W	W	W	W	W	W	W	W	W		
		1	2	3	4	5	6	7	8	9	10	11	12	13	14	15	16		
PHYSICAL ∑																			
History and Physical Exam	X ‡	X		X		X		X		X		X		X		X		X	X
Weight and Performance Status	X	X		X		X		X		X		X		X		X		X	X
Toxicity Notation				X		X		X		X		X		X		X		X	X
Disease Assessment	X									X								X	X
Dermatologic evaluation ~	X					X								X					X
Head and Neck Exam †	X					X								X					X
LABORATORY ∑																			
CBC/Differential/Platelets	X			X		X		X		X		X		X		X			
AST and ALT	X			X		X		X		X		X		X		X			
Serum creatinine/ Calculated creatinine clearance	X			X		X		X		X		X		X		X			
Total bilirubin	X			X		X		X		X		X		X		X			
Magnesium/ Potassium Calcium/Sodium/Bicarb/Chlo ride	X			X		X		X		X		X		X		X			
SPECIMEN SUBMISSION																			
Tissue for BRAF Testing & Banking £																			
Blood £	X									X								X	X
X-RAYS AND SCANS																			
CT or MRI ◊ ☞	X									X								X	X
ECG ♂				X				X				X							
TREATMENT ∑																			
Cetuximab		X		X		X		X		X		X		X		X			
Irinotecan		X		X		X		X		X		X		X		X			
Vemurafenib		X	X	X	X	X	X	X	X	X	X	X	X	X	X	X	X		

Click here for [footnotes](#).

Calendar 9.1, 9.2 and 9.3 footnotes.

- Σ Protocol treatment and parameters will continue at these intervals until progression of disease or until patient has met any of the guidelines in [Section 7.6](#).
- Ω After off treatment prior to disease progression, scans for disease assessment and physical assessments (with lab tests performed at the discretion of the treating investigator) should take place every 8 weeks until progression.
- % After off treatment following disease progression, physical assessments (with lab tests performed at the discretion of the treating investigator) should take place every 6 months for three years from the time of registration to Step 2.
- ¥ Must be done within 28 days prior to registration
- £ Required specimen submission for patients. See [Section 15.1](#) and [15.2](#) for additional information.
- ◇ CT or MRI for disease assessment must be performed every 8 weeks while on study treatment.
- α Patients who progress on Arm 1 may crossover to Arm 3 treatment if criteria in Section 5.3 are met and patient is registered to Step 3 Crossover Registration.

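### Crossover patients can start vemurafenib with no Step 3 ECG, so a QTc above the protocol's own 500 msec hold limit could go unseen

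*Combined protocol and SAP*

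**What the plan says.** **Step 2.** Section 5.2a.10 states: "Patients must have an ECG within 14 days prior to Step 2 Randomization". The same item caps QTc at 500 msec. It applies to both arms.

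**Step 3.** Section 5.3 asks for documented progression on Arm 1, registration within 28 days of stopping Arm 1 treatment, Zubrod 0-1, and adequate blood counts, liver function and kidney function. The laboratory items carry a 14-day window, as in "Patients must have adequate hematologic function as evidenced by all of the following within 14 days prior to Step 3 registration". There is no ECG or QTc item. Section 7.5a says "Patients must be eligible and registered for Step 3 Crossover Registration per" Section 5.3; it does not refer back to 5.2.

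**Calendars.** In "9.1 Arm 1: Cetuximab + Irinotecan" the only ECG is at Step 2. In "9.2 Arm 2: Cetuximab + Irinotecan + Vemurafenib" there is an ECG at Step 2, then at Weeks 3, 7 and 11. In "9.3 Arm 3: Cetuximab + Irinotecan + Vemurafenib" the ECG cell at Step 3 is blank and the first mark is at Week 3, followed by Weeks 7 and 11.

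**Dose rule.** Section 8.3o says "Withhold vemurafenib until QTc interval" is at or below 500 msec. It removes the patient permanently if QTc stays above 500 msec and has risen by more than 60 msec from pre-treatment values, once cardiac risk factors are controlled. Its examples of those factors are "electrolyte imbalances, congestive heart failure, bradyarrhythmias".

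**The concern.** Vemurafenib is new to the patient at Step 3, at the same 960 mg twice-daily dose as in Arm 2. Section 3.3c states that it prolongs QT and can lead to torsade de pointes. Arm 2 patients are screened for this before their first dose; crossover patients are not screened again.

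Two things follow. First, a patient whose QTc rose above 500 msec during Arm 1 meets every item in 5.3 and may start a drug that 8.3o would withhold at that value. Second, the 60 msec removal test in 8.3o needs a pre-treatment value. For Arm 3 the only one the protocol requires was taken before any Arm 1 therapy, so a rise that occurred on Arm 1 could be counted against vemurafenib.

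The omission looks more like an oversight than a choice. In 9.3 the dermatologic and head and neck examinations are both marked at Step 3, and their footnotes name both registration steps. The ECG footnote names neither, and no reason for leaving the ECG out is given.

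**Working it through.** The plan states no figure for the age of the ECG, so there is none to reproduce. The age at first vemurafenib dose is the sum of the windows that the protocol allows.

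**Inputs**
- Step 2 ECG: up to 14 days before randomization (5.2a.10).
- Progression found at a scheduled scan: every 8 weeks on treatment (Section 9 footnotes), so day 56 or day 112, counted here from randomization.
- Stopping Arm 1 to Step 3 registration: up to 28 days (5.3a).
- Registration to first dose: up to five working days (13.1), taken as 7 calendar days.
- Assumption: Arm 1 treatment stops on the day progression is found.

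**Formula:** maximum age at first dose = 14 + scan day + 28 + 7. The minimum, with every window at zero, is the scan day itself.

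| Case | Minimum (days) | Maximum (days) |
|---|---|---|
| Arm 3, progression at 8-week scan | 56 | 14 + 56 + 28 + 7 = 105 |
| Arm 3, progression at 16-week scan | 112 | 14 + 112 + 28 + 7 = 161 |
| Arm 2 | 0 | 14 + 7 = 21 |
| Arm 3 with the Step 2 criterion repeated | 0 | 14 + 7 = 21 |

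Later progression gives older tracings, so 161 days is not a ceiling. If scans are timed from the first Arm 1 dose instead, up to 7 days are added to each Arm 3 maximum without the fix.

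**First check on the drug.** Week 3 begins after 14 days of dosing, or 336 hours. With the 57-hour half-life in Section 3.3b, 336 / 57 = 5.9 half-lives, so plasma levels are close to steady state when QTc is first measured.

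**Number exposed.** Section 11.1 plans 105 randomized patients: 105 / 2 = 52.5, so at most about 52-53 in Arm 1. The randomized count suits a safety question better than the eligible count of 94 / 2 = 47, because Section 11.3 assesses adverse events in everyone who receives a dose.

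**Number affected.** The documents give neither the share who cross over nor the rate of QTc above 500 msec at Step 3. For illustration only, assume 25-75% cross over (52.5 × 0.25 = 13 to 52.5 × 0.75 = 39) and 1-5% of them exceed 500 msec. The expected count is 13 × 0.01 = 0.1 to 39 × 0.05 = 2.0 patients.

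**The case against.** The strongest reply is that 5.3 is a deliberately shortened re-check of patients who already passed Step 2, and that other safeguards cover QT risk. Section 3.3c has the medication list screened before vemurafenib starts. Electrolytes are drawn every two weeks on Arm 1 and again at Step 3. ECGs follow on the same schedule as in Arm 2, and a known QTc above 500 msec would trigger 8.3o. The adverse-effect text for cetuximab and irinotecan does not list QT prolongation, so a new value above 500 msec on Arm 1 should be rare. Sites may also take an ECG unasked.

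Most of this stands, and it is why the number affected is probably very small. But none of these safeguards measures QTc before the first dose, and 8.3o cannot act on a value nobody has taken. The missing electrolyte limit in 5.3 is not itself a crossover gap, since Step 2 sets none either.

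The calendars are supporting evidence only, because table cells can shift when text is extracted. The point rests on the wording of 5.3 and 7.5a, with which the blank cell in 9.3 agrees.

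A reader might infer more than the documents support:
- *That the tracing is at most about 122 days old.* Putting the assumed 2.4-month median (73 days) into the formula gives 14 + 73 + 28 + 7 = 122. This stacks maximum windows on a median. It is not a bound, since half of Arm 1 is expected to progress later, and it is not typical, since progression is documented at scans near day 56 or 112.
- *That the cetuximab hypomagnesemia rates in 3.1c (55%, severe in 6-17%) size the problem.* They describe a risk factor in a mixed colorectal and head and neck population, not patients with QTc above 500 msec.
- *That Arm 3 has no QT monitoring.* It has the Arm 2 on-treatment schedule; only the baseline is missing.

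**Conclusion.** The gap is real, and nothing else in the supplied text closes it. As written, the plan lets a crossover patient start vemurafenib at a QTc for which its own dose rule withholds the drug. The last required tracing is up to about 105 or 161 days old, depending on the scan, against about 21 days in Arm 2.

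Those ages assume that Arm 1 treatment stops at progression, that scans are timed from randomization, and that five working days equal 7 calendar days. The expected count of 0.1 to 2.0 patients rests wholly on assumed rates and shows scale only.

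The primary analysis is unaffected. Crossover requires documented progression, so the Arm 1 PFS event in Section 10.5a has already occurred by Step 3. This is a safety correction that should be made because the possible harm is serious and the remedy is cheap. It is not a threat to the trial's main conclusion.

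**What to change.** 1. Add to Section 5.3 an ECG taken no more than 14 days before Step 3 registration, with QTc of 500 msec or less.
2. Mark the ECG in the Step 3 column of calendar 9.3.
3. State in 8.3o that this ECG is the pre-treatment value for Arm 3.

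The oldest qualifying tracing at first dose then falls to 21 days, the Arm 2 limit.

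**Cost.** Amendment wording, plus one routine ECG per crossover patient (at most about 52-53), at a visit that already includes an examination and laboratory tests. Funding is not assured. The Revision #2 consent change pays for up to 5 additional ECGs for patients on vemurafenib. Under the ECG footnote, a patient who stops after cycle 3 already uses about 3 on treatment plus 2 in the following six months, so the Step 3 tracing could be a sixth.

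A patient with QTc above 500 msec would have crossover delayed, and would lose it if the value is not corrected within the 28 days allowed by 5.3a. That is the purpose of the criterion, but it should be acknowledged.
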